NATIONAL POLYTECHNIC INSTITUTE

School of Medicine

SECTION OF GRADUATE STUDIES AND RESEARCH

“Gene modulation of NLRP3, IL-1 β and TNF- α in peripheral blood of patients with exogenous obesity treated with Berberine.”

Principal Clinical Research

PhD [name]
PhD [name]

Clinical sub-investigator

PhD [name]
Nutritionist [name]

ESM CE-01/7-12-2015

Mexico City, 15 August 2015

ABSTRACT

Background: In the treatment of exogenous obesity more than 800 traditional plants are used, such is the case of *Berberine* a phytopharmaceutical. This phytodrug has been shown to be anti-obesogenic in the Asian population, however its effect on our population is unknown. **Objective:** To determine the effects of *Berberine* on the gene modulation of NLRP3, IL-1 β and TNF- α in peripheral blood of patients with exogenous obesity. 120 patients were studied, treated with: hypocaloric nutritional plan, hypocaloric nutritional plan and moderate aerobic exercise, hypocaloric nutritional plan, moderate aerobic exercise plus *Berberine* and finally a normo-weight group without treatment. Anthropometric measurements, biochemical tests, clinical and gene expression data of NLRP3, IL-1 β and TNF- α were obtained. The anthropometric measurements, the treatment with *Berberina* obtained, with the exception of ICC, statistically significant results, while in the biochemical results the groups 2 and 3 showed similar results, those treated with Berberina only the VLDL

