What is the effect of Berberine on the gene expression of IL-1 β , TNF- α and NLRP3, in peripheral blood cells in individuals with exogenous obesity?

9. Objectives

General objective:

To determine the effects of Berberine on gene expression of cytokines IL-1 β , TNF- α and NLRP3 in individuals with exogenous obesity.

Specific Objectives:

1. To form groups diagnosed with exogenous obesity.
2. To evaluate anthropometric parameters
3. To evaluate biochemical parameters
4. To quantify the expression (mRNA) of NLRP3, IL-1 β and TNF- α
5. To establish the differences in gene expression between individuals with exogenous obesity and control subjects.

10. Hypothesis

Berberine inhibits gene expression of NLRP3, IL-1 β and TNF- α in individuals with exogenous obesity.

11. Material and methods

Type of study:

An experimental, analytical, longitudinal, prospective study of comparative groups was carried out.

Study subjects

Ninety patients with type I and II obesity will be selected, as well as 30 control subjects (healthy adults), who agreed to be donors of a peripheral blood sample, 2 tubes (1: biochemistry, 2: gene expression) channeled to the Obesity Program unit (Comprehensive Medical Service, ESM, IPN), with the following selection criteria.

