The thermocycler was programmed with the following scheme: preincubation for one cycle of 10 minutes at 95°C; the reaction for 45 consecutive cycles (denaturation at 95°C for 10 seconds, annealing at 60°C for 30 seconds and extension at 72°C for 1 second) and the final incubation at 40°C for 30 seconds.

Table 5. Oligonucleotide sequences used to determine gene expression.

Gen	Proteins	Sequences	Concentration
NLRP3	Proteína 3 que contiene dominios NACHT, LRR y PY	F: 5' GCA AGA CTT TGA CAA CAT GC3' R: 3'CAC CTG TTG TGC AAT CTG AAG5'	10nM
TNF- α	Factor de necrosis tumoral alfa	F: 5' CAGCCTCTCTCCCTTGAT3' R: 3'GCCAGAGGGCTGATTAGAGA5'	10nM
IL-1 β	Interleucina 1 beta	F: 5' TTG GGT AAT TTT TGG GAT CTT AC3' R: 3'CTG TCC TGC GTG TTG AAA GA5'	10nM
B-actina	Gen constitutivo	F: 5' AGC CAC ATC GCT CAG ACA C3' R: 3'GCC CAA TAC GAC CAA ATC C5'	10nM

Statistical analysis

The values of each determination are expressed as the mean \pm SE. The differences between the groups were calculated with ANOVA. Differences between the groups will be determined by using Student's T test. In all tests, a value less than or equal to 0.05 was considered significant.

Ethical aspects

The study will be of lower than minimum risk, since no blood was obtained from the participants in quantities greater than the limit established by the Regulations for Research on Human Beings of the General Health Law. The project was evaluated,

approved and accepted by the Research and Ethics Committee of the Higher School of Medicine of the National Polytechnic Institute.

The study was carried out in accordance with the ethical principles:

- Declaration of Helsinki of the WMA - Ethical principles for medical research involving human beings¹²⁶.
- Written and signed informed consent as stipulated in article 21 of the General Health Regulations on Health Research¹²⁷.
- As stipulated in article 17 of the General Health Regulations on Health Research, this project is classified as minimal risk¹²⁷.
- The protocol was carried out in compliance with the recommendations established in NOM-087-ECOL-SSA1-2002, which addresses matters related to Environmental Protection and Environmental Health; Biological-infectious Hazardous Waste¹²⁸.

Material Resources

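### The abstract calls Groups 2 and 3 similar on biochemistry, but the planned analysis (mean and SE, ANOVA, t test, p ≤ 0.05) cannot support a finding of similarity

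*Combined protocol and SAP*

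**What the plan says.** The abstract gives a result for the biochemical panel: "while in the biochemical results the groups 2 and 3 showed similar results". The text then runs on to "those treated with Berberina only the VLDL" and stops, so whatever qualified the statement is not available.

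Under 'Study groups', Group 2 is obese patients on a nutritional plan with moderate aerobic exercise. Group 3 is the same with berberine added. Evaluating biochemical parameters is the third specific objective. The general objective and the hypothesis concern gene expression.

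'Statistical analysis' is one short paragraph. On description: "The values of each determination are expressed as the mean", with the standard error. On testing: "The differences between the groups were calculated with ANOVA" and "Differences between the groups will be determined by using Student's T test". On the decision rule: "In all tests, a value less than or equal to 0.05 was considered significant". It plans no confidence interval for a between-group difference, and it gives no power and no criterion for calling groups alike.

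On size, 'Study subjects' says: "Ninety patients with type I and II obesity will be selected, as well as 30 control subjects". The numbers per obese group are not stated.

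**The concern.** Of the listed group comparisons, Group 3 against Group 2 is the one whose listed interventions differ by berberine alone. A statement that these two groups are similar will be read as a statement about what berberine adds to the biochemistry.

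Under the stated analysis, the statement can rest on one of two things:

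- The Group 3 versus Group 2 test gave p > 0.05. That is failure to detect a difference. How informative it is depends on precision, and the plan does not report precision for the difference.
- Each group was significant on much the same variables. That compares two sets of p-values and never estimates the difference between the groups.

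Either way, a moderate effect of berberine in either direction could sit behind the word 'similar', and a reader could not tell.

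**Working it through.** The plan states no power, effect size or SD, so it has no figure of its own to reproduce. The check asks how precise the Group 3 minus Group 2 comparison can be.

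**Inputs**

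- From the documents: 90 obese patients in three obese groups; threshold 0.05; Student's t test.
- Assumed: an equal split, 90 / 3 = 30 per group; two-sided testing; no baseline adjustment (none is planned); differences in SD units, because no SDs are given.

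**Step 1. Interval width.** In SD units the half-width is t(0.975, 2n − 2) × √(2/n).

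- n = 30: 2.002 × √(2/30) = 2.002 × 0.2582 = 0.517 SD.
- n = 20: 2.024 × 0.3162 = 0.640 SD.
- n = 40: 1.991 × 0.2236 = 0.445 SD.

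At 30 per group, an observed difference of exactly zero gives an interval of about −0.52 to +0.52 SD. This step needs no assumed effect size.

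**Step 2. Miss rate.** With true difference d in SD units, the t statistic follows a noncentral t distribution with 2n − 2 degrees of freedom and noncentrality d × √(n/2). The miss rate is the probability that it falls between −t(0.975) and +t(0.975).

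At n = 30, √(30/2) = 3.873:

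| True difference | Noncentrality | Miss rate |
|---|---|---|
| 0.3 SD | 1.16 | 79% |
| 0.5 SD | 1.94 | 52% |
| 0.8 SD | 3.10 | 14% |

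At 0.5 SD, varying the number analysed per group:

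| n per group | 20 | 25 | 30 | 35 | 40 |
|---|---|---|---|---|---|
| Miss rate | 66% | 59% | 52% | 46% | 40% |

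The difference detectable with 80% power at 30 per group is 0.74 SD.

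**Step 3. The other meaning.** If the abstract means that both groups changed significantly on much the same variables, the miss rates in step 2 do not describe that statement. The conclusion fails for a different reason: two groups can each be significant, or each be non-significant, while their difference is of any size within the interval in step 1.

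**The case against.** The best defence is that this is one clause of a translated abstract, cut off before its qualification. The preceding clause reports significant results for berberine on anthropometry with one exception. Read in parallel, the biochemistry clause may only describe which variables changed in each group, with VLDL set apart. That stands as a caution. The clause may carry an exception or a within-group meaning, and nothing should be concluded from the lost words. It does not rescue the similarity statement, because neither meaning is a finding of similarity.

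A second defence is that 0.5 SD, the equal split and two-sided testing are assumptions. That is also right. A one-sided 0.05 test would miss 0.5 SD about 39% of the time. Baseline adjustment, if it were planned, would reduce the miss rate to 41% or 24% at assumed correlations of 0.5 or 0.7. The interval width depends less on these choices, and the ranges above show how far the miss rate moves.

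A third is that a reader can approximate an interval from the two groups' means and standard errors. That is true, but the plan neither reports such an interval nor uses it to judge similarity.

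Three stronger readings are tempting, and the documents do not support them:

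- *The plan equates non-significance with similarity.* It says only what counts as significant; the step to similarity appears in the abstract.
- *The t test runs only after a significant ANOVA, so misses are more frequent still.* No such order is stated, and any figure for it depends on how far the normal-weight controls differ from the obese groups.
- *The statement gives false reassurance about glucose.* Fasting glucose appears as an entry criterion. The biochemical outcomes are not listed, and VLDL is the only one the abstract names.

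**Conclusion.** The point holds as a criticism of an unsupported conclusion. On either meaning of the sentence, the stated analysis cannot show that Groups 2 and 3 were alike on biochemistry.

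With an assumed 30 per group and no adjustment, differences of about ±0.5 SD remain open even when the observed difference is zero, and a true 0.5 SD difference goes undetected about half the time. 'About half' belongs to that effect size. It is a rate for one variable under one two-sided test, and should not be read as the error rate of a statement about the whole panel. Nor does the check show that the groups differed.

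The matter is worth correcting because it changes what the trial concludes about adding berberine, although biochemistry is a specific objective and not the main hypothesis.

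**What to change.** In 'Statistical analysis', state that for each biochemical variable the Group 3 minus Group 2 difference will be reported with its 95% confidence interval in the variable's own units. State also that p > 0.05 will be reported as no difference shown, and not as similarity.

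In the abstract, replace the similarity statement with the differences and their 95% confidence intervals. Alternatively, if that is what the Group 3 versus Group 2 test gave, say that no statistically significant difference between the two groups was shown. Do not infer similarity from the two groups having the same list of significant variables. If the sentence was meant to describe changes within each group, say so.

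An equivalence margin is not the remedy here: results have already been reported, so a margin chosen now would be post hoc.

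The cost is wording plus intervals computed from data already collected, with no new patients, visits or assays. The downside is a weaker stated conclusion.

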1. INTRODUCCIÓN

Obesity is a systemic, progressive, chronic disease of multifactorial etiology, currently the most important and growing public health problem¹. This pathological condition has been present since remote antiquity, persists and is further increased by genetic and environmental factors, and is currently a pandemic with close links to the main causes of morbidity and mortality².

The process of globalization has brought about changes that have modified customs and habits, but above all, our lifestyle. This has led to a considerable increase in chronic non-communicable diseases, such as obesity³.

According to the Clinical Practice Guideline 'Prevention, diagnosis and treatment of overweight and exogenous obesity', as well as NOM-008-SSA3-2017, for the comprehensive treatment of overweight and obesity, a personalized nutritional plan and physical activity/exercise is the initial basis in the management of this pathology, since lifestyle modification is the basis of treatment. The second option for treatment would be pharmacotherapy and ultimately bariatric surgery, depending on the Body Mass Index (BMI) of each patient^{4,5}.

Despite the advances in the treatment of obesity that Mexico has made in health in recent years, this continues to be a major problem to be solved in the country. This pathology is due to inadequate eating habits and sedentary lifestyles, which implies increasing the efforts of the population/authorities to reduce its prevalence. Therefore, the study proposes the implementation of a nutritional plan, moderate aerobic physical activity, as well as the use of phytopharmaceuticals as an alternative coadjvant therapy for the management of obesity, from a clinical, biochemical and molecular point of view.

2. THEORETICAL FRAMEWORK

2.1. Obesity

“Chronic low-grade systemic inflammatory process due to abnormal secretion of cytokines and other inflammatory factors.”⁶

2.2. Definition

Obesity is defined, according to the World Health Organization (WHO), as an abnormal or excessive accumulation of fat that can be detrimental to health, although this concept has changed over time, from excessive accumulation of body fat, greater than or equal to 20% of body weight, greater energy intake, compared to that used, causing an increase in body weight/adipose tissue or as an unfavorable health condition, caused by a positive energy balance maintained over time, characterized by an excessive increase in body fat deposits and body weight^{7, 8, 9}.

According to the World Health Organization (WHO), obesity is defined as abnormal or excessive accumulation of fat that can be harmful to health. This concept has changed over time, from excessive accumulation of body fat, greater than or equal to 20% of body weight, greater energy intake, compared to that used, causing an increase in body weight/adipose tissue or as an unfavorable health condition, caused by a positive energy balance maintained over time, which is characterized by an excessive increase in body fat stores and body weight^{7, 8, 9}. It is not understood how the concept of obesity has changed. I suggest just leaving the WHO and the most recent or complete. Separate the ideas or definitions with a period.

While NOM 174-SSA1-1998 specifies “a disease characterized by the excess of adipose tissue in the body”, on the other hand, the Official Standard for the Treatment of Obesity in Mexico 2010 defines it as “a disease characterized by the excess of adipose tissue in the body, determined with a BMI equal or greater than 30 kg/m² and 25 kg/m² in subjects with height below average height”¹⁰, determined with a BMI equal to or greater

than 30 kg/m² and 25 kg/m² in subjects with height below the average height¹⁰, and NOM 008-SSA3-2010, for the comprehensive treatment of overweight and obesity, defines it as 'abnormal and excessive accumulation of body fat'. Both, overweight and obesity, are accompanied by metabolic alterations that increase the risk of developing comorbidities such as arterial hypertension, type 2 diabetes, cardiovascular and cerebrovascular diseases, as well as breast, endometrial, colon and prostate neoplasms, among others¹¹. Whatever the definition, there are 3 fundamental components that coincide: excess body fat, higher caloric intake with lower energy expenditure and weight gain.

2.3. Epidemiology of Obesity

Obesity has been recognized as a disease by the WHO in 1979 and is considered the greatest public health problem; since 1960 the prevalence of obesity has been increasing, and our country's transition from infectious diseases and malnutrition to having the first place in childhood obesity and the second place in adult obesity in the world, associating this pathology with other chronic non-communicable diseases^{12,13}.

In 1998, obesity was classified by the WHO as an epidemic, due to the fact that globally, there were more than 1 billion overweight adults and 300 million of these were obese. This epidemic is not restricted to developed societies, in fact, its increase is more rapid in developing countries, such as Mexico where it faces a double challenge together with its malnutrition problems¹⁴.

The WHO reported in 2016, that the prevalence (1975 to 2016) of overweight/obesity worldwide increased to almost double with more than 1900 million adults aged 18 years and older, diagnosed as overweight and of these, more than 650 million are obese. About 39% of adults are overweight (39% men and 40% women); overall, 13% of the world's adult population are obese (11% men and 15% women), in both categories the prevalence is higher in women¹⁵.

The highest prevalence of overweight and obesity was recorded in the adult population in the American continent (overweight: 62% in both sexes; obesity: 26%)¹², with the United States of America (USA) in first place, with the highest obesity rate in the world, and Mexico in second place with 32%¹⁶.

In the specific case of Mexico, data from the OMENT (Mexican Observatory of Noncommunicable Diseases) show that the epidemiological situation in the country has changed in recent decades¹⁷, since malnutrition and infectious diseases were the public health problems¹⁸. Currently we are a nation with greater obesity in adults, by 2015 a report by Obesity Update referred that Mexico had the fastest increase in the world in overweight/obesity, for that year Mexico ranked second in adult obesity with 30.7% and it was projected that by 2030 it will increase to 39%¹⁷.

In 2016 ENSANUT reported that the prevalence of overweight and obesity in women increased with respect to 2012, not only in adults but also in girls and adolescents, where the greatest increase was in rural areas. In the case of the combined prevalence of overweight/obesity in adults over 20 years of age, the data indicate that seven out of 10 adults suffer from this disease (72.5%), this percentage increased vs. 71.2% in 2012. The case of adult women was 75.6%, the increase was higher in rural areas (8.4%) vs. urban areas (1.6%). In men, the combined prevalence was 69.4%, with an increase of 10.5% vs. 2012^{19,20}.

When comparing the abdominal phenotype of obesity in adults >20 years of age was 76.6% with a higher prevalence in the female sex with 87.7% compared to 65.4% in men; the highest proportion of this disease is concentrated in groups from 40 to 79 years of age. In this category, the only significant percentage difference with the ENSANUT 2012 was 4.9 points in the case of the female sex. In other words, 72% of adults continue to be overweight or obese¹⁹. Therefore, there is concern that generations born in recent decades, because of diseases and health damage caused by obesity, may have lower longevity than previous generations¹³.

Figure 1: Comparison of the results of Prevalence of overweight and obesity in adult population in the ENSANUT, 2016.

[figure not shown]

Figure 2: Comparison of the results of Trend of abdominal obesity in adult population in the ENSANUT, 2016.

2.4. Diagnosis and clinical classification

The diagnosis of overweight and obesity should be obtained by anthropometry (weight, height, waist and hip, % body and visceral fat), blood biochemistry, medical clinical history, as well as dietary clinical history^{21,22}.

The diagnosis of obesity is obtained by classifying the body mass index (BMI), i.e. a person's weight in kilograms divided by the square of the height in meters squared. A person with a BMI equal to or greater than 25 is considered overweight and with a BMI equal to or greater than 30 is considered obese⁷.

The Mexican Official Standard 008 SSA3-2016, for the comprehensive treatment of overweight and obesity, makes the modification for the Mexican population according to short stature which, classifies it as a measurement less than 1.50 meters in women and less than 1.60 meters in men¹⁰.

Table 1. Classification of overweight and obesity according to BMI.

Classification	BMI (Kg/m2)	Classification	BMI (Kg/m2)
		Low height	
Normal weight	18.50-24.99		
Overweight	> 25 y <29.9	Overweight	≥ 23 y < 24.9
Obesity		Obesity	≥ 25
Grade 1	30 a 34.99		
Grade 2	35 a 39.9		
Grade 3	≥ 40		

. Table 1. The classification of the degree of obesity using the body mass index as a criterion, distinguishing the following degrees referred to in Table 1: Being obesity as BMI equal to or greater than 30, while with short stature that classifies it as a measurement less than 1.50 meters in women and less than 1.60 meters in men referred to in Table 1, according to the Mexican Official Standard 008 SSA3-2016. Source: WHO and NOM 008.

The clinical classification of obesity is derived in two: exogenous and endogenous^{23,24,25}.

Exogenous: this obesity results from an imbalance between calories consumed and calories expended due to a lack of physical activity, i.e., excessive eating and sedentary lifestyle; exogenous obesity is currently considered the most prevalent not only in Mexico, but in the world^{18,26}.

Endogenous: caused by metabolic alterations, also called intrinsic or secondary^{18,26,27,28}.

Body fat distribution is divided into the following types:

Android (abdominovisceral or visceroportal), there is predominance of adipose tissue in the abdominal area, this type is more frequent in males and is strongly related to cardiovascular risk. Gynecoid (femoro gluteal), predominates in the lower abdomen, hips and buttocks and is more common in women^{18,29,30}. The interest in the genetics associated with the obesity phenotype is due to the variability between individuals, where fat deposition is controlled by gene expression.

(http://reduvirtualcbs.xoc.uam.mx/obesidad/imagenes/m3_imag1.gif)

2.5. Etiology

Obesity is a multifactorial pathology. Obesity-related habits can be divided into two very important fields: genetic and environmental^{31,32,33,34}.

The most influential factor in obesity is the environmental factor, where poor nutrition is fundamental due to the imbalance of energy intake and lack of physical activity. Nowadays it is known that there is a direct relationship with energy intake, since currently unhealthy eating patterns such as the consumption of sugary drinks or industrialized foods, where Mexico has the highest per capita consumption of industrialized beverages,

which are the main causes of malnutrition, and although there have been public policies focused on the reduction of this type of products³⁵, in addition to the intervention in nutritional labeling, tax increase on foods high in sugars, to mention a few^{36,37}, so far they have not been able to reduce in a potential way the national obesity prevalence, but in addition this prevalence has been increasing alarmingly.

There are other possible causes for the development of overweight and obesity that are not modifiable, such as age, genetics, race, ethnicity and sex³⁸. While there are other modifiable causes such as sociocultural: family environment, economic income, educational level, marital status; biological: number of pregnancies (women); behavioral: smoking, alcoholism, depression, anxiety or some other psychopathologies; and those related to physical activity: daily activities, exercise or sport^{39,40}.

Among the genetic causes, genes related to the control of energy intake and use have been characterized and studied, in addition to their polymorphisms^{40,41,42,43}.

In addition, the current lifestyle with insufficient sleep, high stress, excessive use of electronic devices, among others, are the main causes of weight imbalance in Mexicans⁴⁴.

2.6. Comorbidities associated with obesity.

Obesity is considered the main risk factor for the development of other comorbidities, among which are^{45,46}:

Type 2 diabetes: like obesity, diabetes is more prevalent in women and is more prevalent in urban areas than in rural areas^{47,48,48,49,50}. Obesity is related to the causality of type 2 diabetes, with 90% of the prevalence attributed to it, due to the lipotoxicity inherent to prolonged obesity; thus, almost 10% of the Mexican population lives with diabetes, although it is considered that a similar number is undiagnosed. The complications of this disease are the leading cause of mortality in Mexico: every year, 98,000 people die from diabetes worldwide^{48,49,50,51,52}.

Arterial hypertension (AHT): it is fully recognized that obesity is a cardiovascular risk factor independent of the patient's blood pressure; android obesity is the highest risk factor, not only for AHT but also for increasing cardiovascular risk factors and, once again, the female sex has a higher prevalence ^{53,54,55,56,57}.

Dyslipidemias: an adult with obesity is up to four times more likely to be diagnosed with dyslipidemias, compared to an adult with a healthy weight. In Mexico, the measurements recorded in the last 30 years show a trend towards an increase in overweight and obesity^{42,58}.

